**SPECIFIC AIMS**

Concisely state the objectives of the study and the hypothesis being tested.

**Specific Aim 1**

**Allopregnanolone levels are lower in postmenopausal women with treatment-resistant depression (n=20) as compared to those with treatment-responsive depression (n=20) and those with no history of depression (n=20).** We will investigate allopregnanolone levels in a cross-sectional study of 60 postmenopausal women with the hypothesis that allopregnanolone is lower in postmenopausal women with treatment-resistant depression as compared to those with treatment-responsive depression and controls without depression, suggesting that allopregnanolone plays a critical role in treatment responsiveness.

**Specific Aim 2.1**

**Allopregnanolone analog augmentation improves depressive symptoms in women with treatment-resistant depression.** We will investigate in women with treatment-resistant depression whether allopregnanolone analog augmentation leads to a reduction in depressive symptoms, as measured by the *Montgomery-Asberg Depression Rating Scale* and *Clinical Global Impression-Severity* over an 8-week period. *Note that Aim 2.1 is not dependent on Aim 1, as pharmacologic levels of allopregnanolone could still lead to improvement in depressive symptoms even if the Aim 1 hypothesis that physiologic levels of allopregnanolone are lower in women with treatment-resistant depression is not confirmed.*

## BACKGROUND AND SIGNIFICANCE

Provide a brief paragraph summarizing prior experience important for understanding the proposed study and procedures.

Partners Human Subjects Research Application Form

Version Date: October 15, 2014

Major depressive disorder (MDD) is highly prevalent with significant morbidity and is more prevalent in women than men. Approximately 70% of patients do not respond to standard treatment, as demonstrated in the STAR\*D trial, in which only 30% of patients with MDD achieved remission after 8-12 weeks of SSRI therapy despite adequate dosing. Therefore, the identification of an effective, well-tolerated, antidepressant augmentation therapy would have important clinical and public health implications. Steroid hormones and their metabolites act as transcription factors for parent hormone or other neurotransmitter receptors, and in some cases may also directly activate neurotransmitter receptors. Allopregnanolone, a progesterone metabolite, is a potent positive modulator of GABA action at GABAA receptors. Initial studies showed that antidepressant treatment in male rats elevated allopregnanolone levels in the brain. Investigators then demonstrated that human subjects (n=15) with treatment-naïve MDD had CSF allopregnanolone levels that were 60% lower than age- and sex-matched controls without MDD. Moreover, CSF allopregnanolone increased with SSRI treatment, and this normalization of allopregnanolone correlated with improvement in depressive symptoms as measured by the HDRS. Additionally, our own preliminary data demonstrate that allopregnanolone levels are inversely associated with severity of depression and anxiety in women across the weight spectrum, independent of BMI. Preliminary mechanistic explorations into the effects of allopregnanolone in mood disorders have shown alterations in amygdala activity and connectivity between the amygdala and dorsal medial prefrontal cortex that were correlated with reduction in anxiety in some studies. However, in these studies pregnenolone, a parent compound of allopregnanolone that was shown to subsequently increase allopregnanolone levels, was administered and the effect of pure allopregnanolone augmentation itself has not been studied. [REDACTED] has committed to provide Ganaxolone, which is

a synthetic analog of allopregnanolone with an added methyl group which prevents conversion back to the parent compound progesterone, for the proposed pilot study. Ganaxolone has been developed as an anti-epileptic medication and studied in over 1,300 individuals for up to two years in both adults and pediatric populations. Studies have reported only minor side effects, including somnolence, dizziness and fatigue.

Allopregnanolone levels are associated with severity of depression and anxiety in women across the weight spectrum. 36 women of a wide range of weights and depression severity were studied in the follicular phase of the menstrual cycle. Allopregnanolone levels measured by gaschromatography mass-spectrometry (GC-MS) were negatively associated with severity of depression ( $r = -0.45$ ,  $p = 0.03$ ) and anxiety ( $r = -0.37$ ,  $p = 0.04$ ) independent of BMI, with 15% of the variability in depression and 11% of the variability in anxiety symptom severity attributable to allo levels. Of note, there was no association between levels of progesterone, the parent compound of allopregnanolone, and depression or anxiety severity. In conclusion, greater depression and anxiety severity was negatively associated with serum allopregnanolone, but not progesterone, independent of BMI. This supports the hypothesis that neuroactive steroids such as allo may be potential therapeutic targets for depression in traditionally treatment-resistant groups.

Additionally, we have successfully conducted studies of hormone augmentation strategies in women with treatment-resistant depression and have published a pilot study investigating the effects of low-dose testosterone augmentation on treatment-resistant depression in women, which formed the basis of an ongoing, NIH-funded trial and demonstrated a marked improvement in **Montgomery-Asberg Depression Rating Scale (MADRS)** scores at 2 weeks that was sustained through the 8-week period with administration of low-dose testosterone. At this time, we have recruited more than 50 subjects for an ongoing NIH-funded randomized, double-blind clinical trial of low-dose testosterone for treatment-resistant depression in women in follow-up to this pilot study. We hypothesize that the potential antidepressant effects of low dose testosterone are mediated by neuroactive steroids, including allopregnanolone. Moreover, both the pilot and follow-up studies speak to our ability to recruit and study this specific population of women with treatment-resistant depression.

## RESEARCH DESIGN AND METHODS

Briefly describe study design and anticipated enrollment, i.e., number of subjects to be enrolled by researchers study-wide and by Partners researchers. Provide a brief summary of the eligibility criteria (for example, age range, gender, medical condition). Include any local site restrictions, for example, “Enrollment at Partners will be limited to adults although the sponsor’s protocol is open to both children and adults.”

*Subjects:* Aim 1 will study 60 women ages 50-75 in menopause (amenorrhea >1 year or elevated FSH in women with prior hysterectomy). Aims 2.1 and 2.2 will study 10 women with treatmentresistant depression.

### Aim 1 Inclusion Criteria

1. Female, age 50-75
2. Postmenopausal, defined as amenorrhea for greater than one year and/or elevated FSH for women with prior hysterectomy
3. Meet criteria for one of three subgroups:
  - **Treatment-resistant depression** (N=20): MDD diagnosed by the SCID-I/P and with MADRS  $\geq 16$  who are currently treated with an SSRI or SNRI at an adequate dose for at least six weeks. Meet DSM-IV criteria for a current major depressive episode, as assessed by SCID
  - **Treatment-responsive depression** (N=20): Patients with history of MDD treated with an SSRI or SNRI who have achieved remission (MADRS <10)
  - **Controls** (N=20): Patients with no current or past depression by SCID and no history of antidepressant use. Allopregnanolone levels will be measured by GC-MS.

### Aim 1 Exclusion Criteria

1. Serious suicide or homicide risk, as assessed by evaluating clinician
2. Unstable medical illness including cardiovascular, hepatic, renal, respiratory, endocrine, neurologic
3. Substance use disorder active within last six months
4. Psychotic features (current episode or lifetime), as assessed by SCID
5. Laboratory evidence of untreated hypothyroidism
6. Use of hormones (estrogens, androgens or related hormones) within the prior three months

7. Any investigational psychotropic drug within the last two weeks
8. Alanine aminotransferase (ALT) or creatinine  $> 3x$  upper limit of normal.

### **Aims 2.1 and 2.2 Inclusion Criteria**

1. Female, age 50-75
2. Postmenopausal, defined as amenorrhea for greater than one year and/or elevated FSH for women with prior hysterectomy
3. Meet DSM-IV criteria (by SCID) for Major Depressive Disorder
4. Meet DSM-IV criteria for a current major depressive episode, as assessed by SCID
5. MADRS $\geq$ 16 at baseline visit
6. Currently treated with SSRI or SNRI, with or without adjunctive therapy, at an adequate dose for at least six weeks

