### **Aims 2.1 and 2.2 Exclusion Criteria**

1. Serious suicide or homicide risk, as assessed by evaluating clinician
2. Unstable medical illness including cardiovascular, hepatic, renal, respiratory, endocrine, neurologic
3. Substance use disorder active within last six months
4. Psychotic features (current episode or lifetime), as assessed by SCID
5. Laboratory evidence of untreated hypothyroidism
6. If treated hypothyroidism, significant change in levothyroxine dose within the prior three months
7. Use of hormones (estrogens, androgens or related hormones) within the prior three months
8. Any investigational psychotropic drug within the last two weeks
9. In the judgment of the study clinician, unlikely to be able to participate safely throughout the study period (three or more episodes of self-harm in the past year, documented history of poor treatment adherence, or frequent missed appointments ( $>50\%$ ) in the past year)
10. Alanine aminotransferase (ALT) or creatinine  $> 3x$  upper limit of normal.
11. History of a hormone-responsive cancer
12. Receiving strong CYP3A4 inducers or inhibitors or who intend to consume grapefruit products regularly during the study

Briefly describe study procedures. Include any local site restrictions, for example, “Subjects enrolled at Partners will not participate in the pharmacokinetic portion of the study.” Describe study endpoints.

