### **Study visits**

#### **Aim 1**

**Screening Visit/ Baseline Visit (n=120):** A “Screening Visit” will be conducted to determine eligibility for the protocol. It is estimated that 120 women will need to be screened to obtain 60 eligible study subjects (20 with treatment-resistant depression, 20 with treatment responsive depression and 20 controls with no depression). The screening visit and baseline visit are simultaneous, and labs will be drawn if the subject passes the psychiatric assessments and qualifies per above criteria. ○ A physical examination, medical history and urine toxicology

- Psychiatric assessments: SCID and MADRS ○ MGH Anti-depressant history form
- If qualified based on psychiatric assessment, blood draw for ALT, creatinine, cbc, thyroid function tests
- Additional aliquots will be drawn for future testing of allopregnanolone and other hormones **Aim 2**

**Screening Visit (n=20):** A screening visit will take place to determine eligibility for enrollment. Participants will be asked to complete the MGH ATRQ and sign release of information forms to request documentation from prescribing clinicians.

Screening visit testing will include:

- Complete medical history ○ Physical examination, including height, weight and vital signs ○ 0800h Blood draw for ALT, AST, bilirubin, creatinine, CBC, thyroid stimulating hormone (TSH) and FSH
- Urine toxicology
- Urine pregnancy test in women <55 years of age ○ Diagnostic interview with SCID ○ MDD symptom assessment with MADRS
- Completion of the MGH ATRQ

If antidepressant-resistance is confirmed following screening procedures, the subject will be scheduled for a baseline visit approximately 1-2 weeks later.

**Baseline Visit for the Ganaxolone Augmentation Study (n=10):** Eligible subjects will undergo baseline testing immediately before the augmentation phase of the protocol.

Baseline visit testing will include the following. However, the safety labs will not be repeated if the Baseline visit occurs within 6 weeks of the screening visit.

- Weight, vital signs, waist-to-hip ratio, and consumptive habits (alcohol, caffeinated beverages) will be recorded.
- Electrocardiogram
- Neuroactive steroid panel, including allopregnanolone, morning blood cortisol, late night salivary cortisol and 8 a.m. salivary cortisol
- Depression efficacy endpoints: MADRS, HAM-D, IDS-SR and SDQ ○ Cognitive Functioning: CPFQ

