- Persistent/residual symptom assessment: SF-36, BFI, ESS, FSS, DISF, SFQ, GAD-7 ○ Safety assessments: SAFTEE-SI and CHRT ○ We will distribute the Study Drug Compliance and Hot Flash Diary ○ Cognitive testing (Probabilistic Reward and Pattern Separation Tasks) will be performed

**Follow-up Visits (Ganaxolone Augmentation Phase):** Subjects will then receive Ganaxolone therapy. In the case of a drop out, subjects will be asked to come in for an optional close-out visit. This visit will include all of the week 8 measures. Follow-up visits will take place at weeks 1, 2, 4, 6 and 8 post-baseline.

Follow up visits will include:

- Weight and vital signs will be recorded (weeks 1,2, 4, 6, 8 and 10); electrocardiogram will be performed in any subject with bradycardia (HR<60) or tachycardia (HR>100)
- Waist-to-hip ratio (week 8)
- Depression: MADRS, IDS-SR, CGI-S, CGI-I, SDQ (weeks 2, 4, 6, 8 and 10),

- HAM-D (week 8 only) ○ Cognitive Functioning:
- CPFQ (weeks 2, 4, 6, 8 and 10)
- Persistent/residual symptom assessment: SF-36, BFI, ESS, FSS, DISF, SFQ, GAD-7 (weeks 2, 4, 6, 8 and 10) ○ Safety: SAFTEE-SI, CHRT (weeks 2, 4, 6, 8 and 10) ○ Salivary cortisol (week 8)
- Medication management sessions (weeks 2, 4, 6 and 8) ○ Neuroactive steroid panel (week 8)
- Blood draw for ALT, AST, bilirubin (week 8)
- We will distribute the Study Drug Compliance and Hot Flash Diary (weeks 2, 4, 6, and 8) ○ Cognitive testing (Probabilistic Reward and Pattern Separation Tasks) will be performed (week 8 only)
- Measurement of ganaxolone levels

Taper: After the 8-week visit, subjects receiving [REDACTED]

[REDACTED] A 10-week visit will be performed and will include:

- Vital signs ○ Safety: SAFTEE-SI, CHRT ○ Depression: MADRS, IDS-SR, CGI-I
- Persistent/residual symptom assessment: SF-36, BFI, ESS, FSS, DISF, SFQ, SDQ, GAD-7

**3-Month Follow Up Questionnaires:** Three months after the 10-week visit or last visit completed, subjects will be sent the following questionnaires to complete: ○ IDS-SR, BFI, SDQ, GAD-7

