#### **Aim 2**

Subjects will complete a blood draw at all study visits except the week 1 and week 10 visits. This will total 526mL of blood over the approximate 10-week study period from screening to the final visit

For studies involving treatment or diagnosis, provide information about standard of care at Partners (e.g., BWH, MGH) and indicate how the study procedures differ from standard care. Provide information on available alternative treatments, procedures, or methods of diagnosis.

Subjects being studied in this protocol will still have at least moderate depression. Standard care alternatives are presented in the Consent form. Subjects at MGH are offered three months of free medication management clinic services for depression treatment after completion of a clinical trial such as this one. Research staff will assist in arranging subsequent treatment by providing referrals and communications to subsequent providers.

Describe how risks to subjects are minimized, for example, by using procedures which are consistent with sound research design and which do not unnecessarily expose subjects to risk or by using procedures already being performed on the subject for diagnostic or treatment purposes.

The procedures to protect against or minimize potential risks include the following: (1) the assignment of unique study subject numbers to patients, (2) the use of these primary identifiers throughout the study, (3) storage of information in locked file cabinets, and (4) access limited to study personnel for these file cabinets and data.

We have set up exclusion criteria to minimize risks:

- Subjects must be medically stable as defined in this protocol.
- We exclude people who may be considered particularly vulnerable in clinical trials, including those at acute risk for suicide, those with active substance abuse or dependence, and those with psychosis (or treated with antipsychotic medications).
- Because we are investigating the efficacy of a hormone, it will be important to exclude patients with other endocrine abnormalities which could contribute to treatment resistance or with a changing endocrine status.

Study Subjects will be discontinued from the study if they:

- a. Score a 6 or 7 on the CGI-I on 2 consecutive study visits

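### Aim 2 sets a minimum time on adequate antidepressant treatment but no rule that background treatment be unchanged, so a response to a background change could not be separated from ganaxolone

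*Protocol*

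**What the plan says.** Protocol, Aims 2.1 and 2.2 Inclusion Criteria, item 6: "Currently treated with SSRI or SNRI, with or without adjunctive therapy, at an adequate dose for at least six weeks".

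The Aims 2.1 and 2.2 Exclusion Criteria list 12 items. Item 6 is a stability rule for one background drug: "If treated hypothyroidism, significant change in levothyroxine dose within the prior three months". The only psychotropic look-back is item 8: "Any investigational psychotropic drug within the last two weeks". The risk-minimisation text after Blood collection says that vulnerable people are excluded, among them "those with psychosis (or treated with antipsychotic medications". The Aim 2 exclusion list has an item for psychosis but none for antipsychotic treatment.

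Under Study visits, the Aim 2 screening visit collects treatment history: "Participants will be asked to complete the MGH ATRQ and sign release of information forms". If resistance is confirmed, "the subject will be scheduled for a baseline visit approximately 1-2 weeks later". Then: "Subjects will then receive Ganaxolone therapy". No comparison arm is described.

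Specific Aim 2.1 asks "whether allopregnanolone analog augmentation leads to a reduction in depressive symptoms", on the MADRS and CGI-S over eight weeks. The SAP justifies n=10 from a testosterone pilot (10.7 MADRS points, SD 7.5) and says that the result will supply an effect size for later power calculations. It names no test and no handling of background changes.

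**The concern.** In a before-after study each woman is her own control, so anything else that moves her MADRS between baseline and week 8 is read as treatment effect. Background antidepressant treatment acts on that same scale. Item 6 asks whether it has been adequate for long enough, not whether it has been constant. The protocol accepts the principle of a stable background for thyroid replacement but does not extend it to the treatment closest to the endpoint.

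Two things are at stake: the answer to Aim 2.1, and the effect size handed on to the design of the next trial. There is no randomised comparison to balance background changes and no planned analysis to reveal them.

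**Working it through.** **Step 1. What item 6 admits.** The phrase on duration can be attached to the SSRI/SNRI only, or to the adjunct as well.

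| Case | Duration covers SSRI/SNRI only | Duration covers adjunct too |
|---|---|---|
| Long adequate, dose raised a week before baseline | admitted | admitted |
| Long adequate, dose lowered but still adequate | admitted | admitted |
| Adjunct started a few days before baseline | admitted | not admitted |
| Long-standing adjunct, dose just changed but still adequate | admitted | admitted |
| Any change during weeks 0-8 | not addressed | not addressed |

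The ambiguity decides only the third row. On both readings the item is a minimum duration, not a no-change rule.

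**Step 2. Whether other text closes the gap.**
- Exclusions: none of the 12 items concerns a recent change of antidepressant or adjunct.
- Antipsychotics: the risk text narrows the possible adjuncts, but the exclusion list does not carry it, and other adjuncts have no window.
- Screening records: these serve to confirm resistance. No stability criterion is attached, and they are requested before the 1-2 week gap to baseline.
- MADRS of at least 16 at baseline (inclusion item 5): this removes a woman who has already improved below 16. It does not remove one whose change is too recent to have acted.
- Follow-up visits: medication management sessions are scheduled at weeks 2, 4, 6 and 8, without saying whether background treatment may change or how a change is recorded.
- Redactions: these affect the taper, ganaxolone dosing and the end of the risk text. The eligibility lists show none.

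**Step 3. The SAP's own figure.** The SAP calls power ample but gives no number. I assume a one-sample t-test on MADRS change, two-sided alpha 0.05, and that 7.5 is the SD of the change.
- Noncentrality = (10.7 / 7.5) × √10 = 4.51, giving power of 97.9%. This is consistent with the SAP's word, and the present point does not alter it.
- Smallest significant mean change = 2.262 × 7.5 / √10 = 5.4 points.

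**Step 4. Size of a background shift.** If k of 10 women each shift by d points, the mean shifts by k × d / 10. Both k and d are assumptions; the documents give neither.
- k = 1, d = 5: 1 × 5 / 10 = 0.5 points; 0.5 / 10.7 = 5% of the SAP's figure.
- k = 3, d = 10: 3 × 10 / 10 = 3.0 points; 3.0 / 10.7 = 28%.

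The sign follows the change: intensification adds to apparent improvement, and reduction could subtract from it.

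**Step 5. Effect on a significance test if ganaxolone did nothing.** Simulation with n=10 and SD 7.5 gives the chance of a significant improvement, against a nominal 2.5% in that direction:

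| Women affected | Points gained by each | Mean shift | Chance |
|---|---|---|---|
| 1 | 5 | 0.5 | 3.5% |
| 3 | 5 | 1.5 | 6.9% |
| 3 | 8 | 2.4 | 10.2% |

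No shift in the assumed range reaches the 5.4-point threshold alone. The main harm is to the estimate, where any shift enters point for point.

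**The case against.** The strongest reply is that nothing shows any woman had, or would have, a recent change. A reader might infer from item 6 that such improvement is being counted as ganaxolone effect, and always in its favour. The documents do not support that. They show that the rule permits such a change, not that one happened, and item 6 equally admits a recent reduction, which could work against ganaxolone. This part of the reply stands in full.

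A reader might also infer that adjuncts have no time requirement at all. The wording allows the six weeks to cover them, so that is too strong. It is also unstated whether adjunctive therapy includes psychotherapy.

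The reply can further point to existing safeguards: the confirmation of resistance from records, the baseline MADRS threshold and the exclusion of antipsychotic treatment in the risk text. Each narrows the gap, but none requires constancy.

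Two more objections stand. The size range is set by its inputs: ten points per woman is nearly the SAP's whole 10.7, in women selected as treatment-resistant, and the 10.7 itself comes from a different drug. And in an uncontrolled pilot, placebo response and regression to the mean stay mixed with the drug effect whatever the stability rule.

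What does not stand is that the gap is mere missing detail. A site following item 6 exactly could enrol a woman whose antidepressant dose had just been raised, and the design could not detect the consequence.

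**Conclusion.** The point holds as a gap in eligibility and recording, with a conditional consequence. That item 6 lacks a no-change requirement, and that no legible text supplies one, is clear from the wording. Bias arises only if background treatment changes near baseline or during weeks 0-8, and its direction depends on the change. The 0.5 to 3.0 points (5% to 28% of 10.7) is an illustration from assumed inputs, not an estimate. The SAP's sample-size statement is unaffected. The amendment should be made because it is cheap and the estimate is meant for reuse, but it removes one source of bias among several.

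**What to change.** 1. Amend item 6 so that the SSRI/SNRI dose and any adjunctive treatment must have been unchanged for a stated window before baseline. The length of the window is the sponsor's clinical decision. State whether the rule covers psychotherapy.
2. Check it against the ATRQ and prescriber records already requested. Reconfirm with the participant at baseline, because screening records cannot cover the interval since screening.
3. Record any change in background treatment in weeks 0-8 at the existing visits, and state in the protocol how such changes are to be treated.
4. In the SAP, report MADRS change for all women and, as a sensitivity analysis, without those who had a change. Keep the all-women result as the main one: a change after baseline may itself be prompted by poor response, so leaving those women out can select responders.
5. Reconcile the risk text on antipsychotic treatment with the Aim 2 exclusion list.

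Cost: a short protocol amendment, one added item at existing visits and a little more analysis. Some candidates may be delayed or become ineligible. Placebo response and regression to the mean are not addressed and should be named as limitations wherever the effect size is reused.
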